## **12.3 Amplifi System Unplanned Stoppages, Malfunctions, and Potential Device Deficiencies**

All Amplifi System unplanned stoppages, including Pump stoppages, that occur and are observed during the Study, whether they are associated with an AE, ADE, SAE, SADE, or USADE, shall be documented by the Investigator and other Site Personnel by submitting a completed CRF in the Study EDC System.

All Amplifi System malfunctions and deficiencies that are related to the identity, quality, durability, reliability, safety, or performance of the Amplifi System that occur and are observed during the Study, whether they are associated with an AE, ADE, SAE, SADE, or USADE, shall

be documented by the Investigator and other Site Personnel by submitting a completed CRF in the Study EDC System. The Medical Monitor shall adjudicate device relatedness in accordance with protocol definitions.

## **12.10 Reporting**

### **12.10.1 Reporting of AEs**

Investigators will report AEs or suspected AEs to Sponsor as soon as possible after learning of the event by submitting a completed CRF through the Study EDC System. Investigators will report AEs or suspected AEs to Sponsor regardless of whether they are related to the Amplifi System or Study.

Investigators will characterize AEs or suspected AEs as unrelated, possibly related, probably related, or definitely related to the Amplifi System on the AE CRF, using the relational criteria summarized in **Section 12.2 Classification of Adverse Events**.

Investigators will report AEs or suspected AEs to the Central ECEC, in accordance with the Central ECEC requirements.

### **12.10.2 Reporting of ADEs**

The Medical Monitor will report ADE adjudication decisions to the Investigator and Sponsor or Sponsor delegate in accordance with the charter.

Investigators will report ADEs to the Central EC in accordance with the Central EC requirements.

### **12.10.3 Reporting of SAEs**

Investigators will report SAEs or suspected SAEs to the Sponsor (or Sponsor delegate) as soon as possible, preferably within 24 hours, but no later than two (2) working days of the Investigator or Site Personnel becoming aware of an SAE or suspected SAE, by:

- calling Sponsor;
- emailing Sponsor;
- submitting a completed CRF through the Study EDC System, including documentation of the call and email to Sponsor or Sponsor delegate;

Investigators will report SAEs or suspected SAEs regardless of whether they are related to the Amplifi System or Study.

After notifying Sponsor or (Sponsor delegate) and Medical Monitor of an SAE or suspected SAE, Investigators will provide a written report of the SAE or suspected SAE to Sponsor within five (5) working days of the SAE or suspected SAE through the Study EDC System. Investigators will also transmit the written report to the Medical Monitor in accordance with the charter.

Investigators will report SAEs or suspected SAEs that, in their opinion, possibly related, probably related, or definitely related to the Amplifi System to the Medical Monitor for adjudication as SADEs through the Study EDC System, using the relational criteria summarized in **Section 12.3**.

Investigators will report SAEs or suspected SAEs to the Central EC, in accordance

## Clinical Protocol FIH-3

Doc No: CLINP1837  
Revision: D  
DCO No: 25-009  
Effective Date: 02/06/25

with their local EC requirements. Sponsor will report all SAEs and communicate relevant SAE information to the appropriate regulatory agencies and bodies in accordance with relevant local, regional, and national regulatory requirements.

### 12.10.4 Reporting of SADEs

The Medical Monitor will report SADE adjudication decisions to the Investigator and Sponsor or Sponsor delegate in accordance with the charter.

The Medical Monitor will report SADEs to the Central EC in accordance with EC requirements.

Sponsor will report all SADEs and communicate relevant SADE information to the appropriate regulatory agencies and bodies in accordance with relevant local, regional, and national regulatory requirements.

### 12.10.5 Reporting of USADEs

Investigators will report SAEs or suspected SAEs that are characterized by the Investigator as possibly, probably, or definitely related to the Amplifi System, and also characterized as possibly, probably, or definitely a SADE, to Sponsor (or Sponsor delegate) as soon as possible, preferably within 24 hours, but no later than two (2) working days after Investigator or other Site Personnel becoming aware of a USADE or suspected USADE, by:

- calling Sponsor;
- emailing Sponsor;
- submitting a completed CRF through the Study EDC System, including documentation of the call and email to Sponsor; and

After reporting a USADE or suspected USADE to Sponsor, Investigators will provide a written report about the USADE or suspected USADE to Sponsor within five (5) working days after Investigator or other Site Personnel becoming aware of the USADE or suspected USADE.

With Sponsor communication, Investigators will also report USADEs or suspected USADEs to the Central EC, in accordance with the EC requirements.

Sponsor will report all USADEs and communicate relevant USADE information to the appropriate regulatory agencies and bodies in accordance with relevant local, regional, and national regulatory requirements.

### 12.10.6 Reporting of Amplifi System Unplanned Stoppages and Malfunctions

Investigators will report all Amplifi System unplanned stoppages or malfunctions (including component malfunctions) on the appropriate CRF and to Sponsor as soon as possible, preferably within 48 hours, but no later than three (3) working days after Investigator or other Site Personnel becoming aware, by:

- calling Sponsor;
- emailing Sponsor; and
- submitting a completed CRF through the Study EDC System, including documentation of the call and email to Sponsor.

After notifying Sponsor (or Sponsor delegate) and Medical Monitor of an Amplifi System unplanned stoppage or malfunction, Investigators will provide a written report of the Amplifi System unplanned stoppage or malfunction to Sponsor and Medical Monitor within five (5) working days of the unplanned stoppage or malfunction through the Study EDC System.

Investigators will also report all Amplifi System unplanned stoppages and malfunctions to the Central EC in accordance with the EC requirements.

Sponsor will report all Amplifi System unplanned stoppages and malfunctions to the appropriate regulatory agencies and bodies in accordance with relevant local, regional, and national regulatory requirements.

## **14.0 Data Analysis and Statistical Considerations**

### **14.1 Study Size Calculation**

This study is not powered for a specific outcome, given the small number of Subjects in the study. Rather, the goal of this study is to collect additional data on multiple effectiveness and safety measures as described in **Section 4.1 Study Objectives**.

The effectiveness measure of the Study is to determine percent change in cephalic vein diameter from baseline examination (pre-treatment ultrasound) to end treatment (immediately prior to Amplifi System removal and AVF creation, with Amplifi System running at final speed). The Sponsor reviewed results of Amplifi System treatment during the First-in-Human Study and determined that up to ten (10) Inpatient Subjects would be sufficient to evaluate the safety and effectiveness of the Amplifi System.

### **14.2 Statistical Methods**

#### **14.2.1 Demographic and Baseline Characteristics**

Demographic and baseline characteristics will be summarized descriptively using the number of available observations (n), means, standard deviations, medians, minimum, and maximum values for continuous variables, and frequencies and percentages for categorical variables.

#### **14.2.2 Analysis of Effectiveness Measures**

In general, descriptive statistics will be provided. Categorical variables will be summarized using frequencies and percentages of Subjects in each category. Continuous variables will be summarized using descriptive statistics and 95% confidence intervals for means will be computed where appropriate. Statistical modeling will be used to identify potential predictors of treatment success as well as safety events and effectiveness.

A subgroup analysis will be performed for patients who received Amplifi System treatment but have Amplifi System stoppage and AVF creation prior to the specified treatment duration. Patients who received Amplifi treatment at the specified treatment duration (e.g., completed the maximum treatment duration (i.e., 72 hours) without having an AVF created will be reported,

along with the reasons for not having one (e.g., inadequate vein diameter, other factors).

#### **14.2.3 Analysis of Safety Measures**

All safety data for the Subjects will be summarized descriptively and the number of AEs, ADEs, SAEs, and SADEs will be reported as a single group. The AEs, ADEs, SAEs, and SADEs will be grouped by type, and the number and percentage of Subjects experiencing each type will be reported as a single group. An assessment of the severity and causative relation to Amplifi System placement, treatment, and removal, and Study AVF creation and use for each AE, ADE, SAE, and SADE will be reported.

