## **12.1 Definitions**

### **12.1.1 Adverse Events**

An adverse event (AE) is defined as any untoward medical occurrence, unintended disease or injury, or untoward clinical sign or abnormal lab finding in a Subject, regardless of whether the AE was related to the Amplifi System or Study. Stable, chronic, pre-existing conditions will not be categorized as AEs. However, worsening of these conditions occurring during the Study Period may be categorized as AEs.

Investigators will categorize AEs or suspected AEs as unrelated, possibly related, probably related, or definitely related to the Amplifi System using the relational criteria summarized in **Section 12.2 Classification of Adverse Events**.

Investigators will document all AEs and suspected AEs occurring during the Study Period on the appropriate CRF regardless of whether the AE or suspected AE was related to the Amplifi System or Study. Documentation of the AE or suspected AE will include the characterization of the likelihood the AE was related to the Amplifi System.

Investigators will follow all AEs or suspected AEs until they have resolved, have a stable level of sequelae or, in the Investigator's opinion, are no longer clinically relevant.

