### 12.2.6 Potential Adverse Events and Serious Adverse Events

AEs and SAEs that may occur during the placement, operation, use, or removal of the Amplifi System, or the subsequent creation and use of an AVF made with a vein treated with the Amplifi System have been identified during the Amplifi System risk analysis process, included in the Amplifi System risk analysis documents, and are summarized here:

- death;
- vascular injury;
- bleeding;
- pneumothorax;
- air embolism;
- vascular thrombosis;
- thromboembolism;
- hemolysis;
- anemia;
- thrombocytopenia;
- Inflow Catheter and Distal Outflow Catheter dislodgement;
- Amplifi System component fracture or laceration;
- Inflow Catheter and Distal Outflow Catheter tunnel or skin exit site infection;
- Amplifi System thrombosis;
- Amplifi System component failure or replacement;
- unplanned re-hospitalization or prolonged hospitalization;
- unplanned surgery or interventional procedure;
- AVF bleeding or thrombosis;
- AVF infection;
- ipsilateral vascular access steal syndrome after creation of an AVF;
- AVF aneurysm or pseudoaneurysm formation;
- allergic reaction; and
- drug toxicity.

AEs and SAEs that may occur during the placement, operation, use, or removal of the Amplifi System, or the subsequent creation and use of an AVF made with a vein treated with the Amplifi System may be related to:

- testing required prior to Amplifi System treatment;
- the Amplifi System placement procedure;
- the operation and use of the Amplifi System;
- procedures where the Amplifi System is evaluated, such as venography;
- the Amplifi System removal procedure;
- surgery to create a Study AVF; and

- cannulation of a Study AVF.

AEs and SAEs that may occur during the placement, operation, use, or removal of the Amplifi System, or the subsequent creation and use of an AVF made with a vein treated with the Amplifi System may or may not be related to the Amplifi System, based on the relational criteria summarized in **Section 12.2 Classification of Adverse Events**.

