#### **12.2.2 Relational Criteria**

Investigators will document their opinion of the likelihood of the relationship of all adverse events to the Amplifi System using the criteria summarized below:

- *Unrelated*: a temporal relationship between the adverse event and the placement, use, or removal of the Amplifi System is not clear, or there is evidence of potential alternative causes for the adverse event such as concurrent medication or illness
- *Possibly related*: a temporal relationship between the adverse event and the placement, use, or removal of the Amplifi System is not clear and potential alternative causes for the adverse event such as concurrent medication or illness are possible
- *Probably related*: a temporal relationship between the adverse event and the placement, use, or removal of the Amplifi System is clear and potential alternative causes for the adverse event such as concurrent medication or illness are possible but unlikely
- *Definitely related*: a temporal relationship between the adverse event and the placement, use, or removal of the Amplifi System is clear and no potential alternative causes for the adverse event such as concurrent medication or illness are possible

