- providing Sponsor with the Study documents and records necessary for a complete review of the work related to the Study at the Site by Investigator;
- meeting all Study reporting obligations, including:
  - reporting actual or suspected Amplifi System deficiencies, malfunctions, or

- unplanned stoppages to Sponsor, as specified in **Section 12.10 Reporting**;
- reporting actual or suspected AEs, SAEs, SADEs, and USADEs to Sponsor, as specified in **Section 12.10 Reporting** and submitting accurate, complete, and timely adverse event reports to Sponsor; and
- submitting all other reports to the Sponsor that are required,
- grading adverse events using the scale summarized in **Section 12.2 Classification of Adverse Events**;
- determining whether, in the opinion of the Investigator, an adverse event is related to the Amplifi System or Study procedures or surgeries using the criteria summarized in **Section 12.2 Classification of Adverse Events**;
- determining whether, in the opinion of the Investigator, an Amplifi System-related complication is an Amplifi System-related major complication;
- following all known and suspected AEs, ADEs, SADEs, and USADEs until they have resolved, have a stable level of sequelae, or, in the Investigator's opinion, are no longer clinically relevant;
- understanding and accepting the obligations of continuing review by their local EC while conducting the Study, including notifying their local EC of any changes to the Protocol per their local EC requirements, and submitting required reports to their local EC;
- reporting deviations from the Protocol to the Sponsor, as specified in **Section 10.9 Protocol Deviations and Investigator and Site Suspension and Termination**;
- notifying their local EC of Protocol deviations in accordance with their local EC requirements;
- reporting known and suspected AEs, SAEs, SADEs, and USADEs to their local EC in accordance with their local EC requirements;
- understanding and complying with all applicable local, regional, and national regulatory requirements while conducting the Study;
- communicating SAE, SADE, and USADE information and reporting all SAEs, SADEs, and USADEs to the appropriate regulatory agencies and bodies in accordance with relevant local, regional, and national regulatory requirements;
- recording the reason for withdrawal in source documentation and on the appropriate CRF for Subjects that withdraw from the Study;

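### Section 14.2.3 promises each event's relation to device placement, treatment, removal, and AVF creation and use, but the criteria and recording text give one pooled device rating

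*Protocol*

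**What the plan says.** Two places in the protocol ask for attribution by source. Section 14.2.3 states that "causative relation to Amplifi System placement, treatment, and removal, and Study AVF creation and use for each AE, ADE, SAE, and SADE will be reported". Section 15.2 makes the Investigator responsible for deciding whether "an adverse event is related to the Amplifi System or Study procedures or surgeries using the criteria summarized in" Section 12.2.

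The places that define and record the attribution ask for less:

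- Section 12.2.2 (Relational Criteria) opens: "Investigators will document their opinion of the likelihood of the relationship of all adverse events to the Amplifi System using the criteria summarized below". Its four levels name the device's placement, use and removal together. Definitely related, for instance, begins "a temporal relationship between the adverse event and the placement, use, or removal of the Amplifi System is clear and no potential alternative causes".
- Section 12.1.1: "Documentation of the AE or suspected AE will include the characterization of the likelihood the AE was related to the Amplifi System". Section 12.2.3 says the same for SAEs.
- Section 12.10.1: "Investigators will characterize AEs or suspected AEs as unrelated, possibly related, probably related, or definitely related to the Amplifi System on the AE CRF".

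Section 12.2.6 recognises "surgery to create a Study AVF" and cannulation as sources of events alongside placement, operation and removal, but then refers the reader to the same criteria.

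On timing, Section 4.3 has AVF creation follow device removal immediately. In Section 4.5 the major device-related event measure runs from implantation to 30 days after removal and AVF creation.

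**The concern.** The protocol fixes both the output and the judgement that should feed it, and the two do not match. This is not a detail that can wait for the SAP. An SAP can lay out tables, but it cannot supply attributions that Investigators were not asked to make when the event occurred.

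The gap falls where attribution is hardest. Removal and AVF surgery share a session, an arm and a vein, so bleeding, thrombosis or infection afterwards may come from the device, the surgery or both. The Appendix 1 definition of local infection, which is a component of the major-event composite, covers the catheter exit sites and the AVF incision alike. If only device relatedness is rated, an event judged surgical leaves no positive record of that judgement. At stake is the device-related event rate in a study meant to confirm safety.

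**Working it through.** The check is a comparison of passages; apart from one proportion, no arithmetic applies.

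**1. Relations promised against relations rated**

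- Promised in Section 14.2.3: 5 sources per event (placement, treatment, removal, AVF creation, AVF use).
- Rated with criteria (12.2.2) and stated for the AE CRF (12.10.1): 1, the Amplifi System, with its three phases pooled.
- Named as an Investigator duty without criteria of its own (15.2): 1 more, study procedures or surgeries.
- Promised sources with their own rating in the protocol text: 0 of 5.

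**2. The scale applied to an event after the combined session**

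Take an event in the treated arm whose timing relative to removal is clear and for which AVF surgery is a plausible cause, not an unlikely one. Assume the Investigator treats the surgery as an alternative cause. The criteria mention medication and illness only as examples, so this reading is open.

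- Unrelated needs unclear timing **or** evidence of another possible cause: met through the second condition.
- Possibly related needs unclear timing **and** other causes possible: not met, because timing is clear.
- Probably related needs clear timing and other causes possible but unlikely: not met, because surgery is not unlikely.
- Definitely related needs clear timing and no other possible cause: not met.

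Read literally, only Unrelated fits. If timing is judged unclear, Unrelated and Possibly related both fit, and the text does not say which prevails.

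**3. What follows from that rating**

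Section 12.2.2 (Device Adverse Events) and Section 12.2.4 send an event to the Medical Monitor for adjudication as a device effect when the Investigator has rated it possibly, probably or definitely related. An event rated Unrelated does not take that route. Section 4.5 counts device-related events, so the event can drop out of the rate with no record that surgery was the reason.

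**4. Size**

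The protocol gives no figure for how many events would be affected. With the full ten Subjects, one Subject gained or lost changes a Subject-level rate by 1/10 = 10 percentage points; with fewer Subjects the change is larger.

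**The case against.** The strongest case on the other side is that this is a mismatch of wording between sections, in a descriptive study of at most ten Subjects whose events can be reviewed one by one. Its parts deserve separate answers.

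- **Investigators are not confined to one relation, since Section 15.2 names a second.** This stands. The defect is that the second relation has no criteria and no stated place on the form.
- **A reader might infer that device harm cannot be separated from AVF surgery at all.** The documents do not support that. The scale weighs alternative causes, and the Medical Monitor adjudicates device effects. Appendix 1 excludes thrombectomy during AVF creation from major thrombosis and thromboembolism, and AVF or graft creation from major surgery and major interventional procedure. Cannulation complications are a separate measure. The separation is partial, not absent.
- **Joint causes can be recorded, because Possibly and Probably related both allow another cause.** This is true within limits: the first requires unclear timing, the second an unlikely alternative.
- **The Medical Monitor still sees serious events.** Section 12.10.3 does send written SAE reports to the Medical Monitor, but adjudication as a device effect is again tied to a rating of possibly related or higher.
- **The CRF is not shown and may hold more fields.** This is fair, since the recording text is not worded as exhaustive. Extra fields would still lack criteria in Section 12.2.2.
- **Section 14.2.3 may mean two relations, device and AVF, rather than five.** That is a possible reading. Even so, the AVF relation has no criteria.
- **A reader might infer that nearly all events are affected, because most of the safety window falls after removal.** That is a share of calendar days. The documents give no event timing, and some major-event definitions, such as hemolysis and thrombocytopenia, are confined to the treatment period.

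**Conclusion.** The inconsistency is real and worth correcting. As described, the rating does not support the attribution by source in Section 14.2.3, and relation to AVF surgery is not positively recorded. The criteria also allow an event with both device and surgical causes to be rated Unrelated, to bypass adjudication and to leave the device-related count.

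This rests on three assumptions: the AE CRF holds what the protocol text describes and no further relatedness fields; an Investigator may treat AVF surgery as an alternative cause; and the device-related status that the major-event measure uses follows the Investigator's rating and the Medical Monitor's adjudication. The effect on the rate could be zero or several Subjects and cannot be narrowed from the documents. Because the study is descriptive and partial safeguards exist, this is an inexpensive improvement to make before enrolment and not a flaw that undermines the study.

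**What to change.** - In Section 12.2.2 and on the AE CRF, record separate ratings, more than one allowed, at least for the Amplifi System (ideally split into placement, treatment and removal), Study AVF creation and Study AVF use, each with criteria.
- Reword Unrelated so that a possible AVF-surgery cause alone does not make an event device-unrelated, and give events with clear timing and a plausible alternative cause a level above Unrelated. Without this, extra fields would not help: device and surgery could each serve as the other's alternative cause, and both be rated Unrelated.
- Send every event rated possibly device-related or higher to Medical Monitor adjudication, whatever its AVF rating.
- In Section 14.2.3, tabulate device-only, AVF-only and joint events.
- Align Sections 12.1.1, 12.10.1 and 15.2 with the new ratings.

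The cost is a few more CRF fields per event, one table, and a device-related count that may rise slightly because joint events stay in. Cutting Section 14.2.3 back to the single relation now rated would also remove the contradiction, more cheaply, but joint events would stay invisible. Attribution is hard to recover reliably afterwards, so separate ratings are the better choice.
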